### 5.3 LIFESTYLE CONSIDERATIONS

Warfarin arm:

- Consumption of consistent quantities of vitamin K containing food from day to day will assist in the maintenance of your INR in the therapeutic range. (Patients will be provided a copy of the Mayo Clinic booklet on dietary regulation in warfarin treated patients as a guide.)

### 5.4 SCREEN FAILURES

Screen failures are defined as participants who consent to participate in the clinical trial but are not subsequently randomly assigned to the study intervention or entered in the study. An example of a screen failure is someone who is diagnosed with newly recognized dementia or intracerebral hemorrhage following the administration of the baseline neurocognitive assessment and brain MRI. Information on screen failures will be collected for purposes of reporting as follows: demography, eligibility criteria, reason for screen failure and any serious adverse event.

Individuals who do not meet the criteria for participation in this trial (screen failure) will not be rescreened.

## 5.5 STRATEGIES FOR RECRUITMENT AND RETENTION

1. This is a single center study that will be conducted at the Mayo Clinic, Rochester, MN. Target study sample is total of 280 patients. Assuming a screen failure rate of 20%, target accrual is 350 participants. Accrual will be completed in 1 year. The last patient will complete follow-up 2 years later.
2. In order to enrich the study for the population at risk of the primary end point, at least 50% of the enrollees will be >70 y of age.
3. Participants will be identified using two strategies: (1) Individuals with AF living in the 8 counties of Southeast Minnesota (Dodge, Fillmore, Goodhue, Houston, Olmsted, Mower, Wabasha and Winona counties) will be screened for eligibility. Such patients will be identified using the record linkage system of the Rochester Epidemiology Project and Mayo Clinic, Rochester clinical records. Potential participants with AF diagnosed in Olmsted county have already been identified through prior work the investigators have done. (2) Individuals seen in the inpatient and outpatient clinics at Mayo Clinic, Rochester, MN with a diagnosis of AF will also be screened for eligibility. Such patients will be identified by the treating physician, using screening of their medical records and through the Mayo ECG laboratory which flags patients with new identification of AF.
4. Potential participants will be approached using one or more of the following: (1) direct patient contact in the clinic or hospital, (2) through letters and (3) phone calls.
5. The ECG documentation of AF will be confirmed using review of the medical records. Eligibility for the study will be determined first using medical records and confirmed by direct interview of the patient prior to enrollment.
6. Participants will be compensated for their participation in the study as follows: (1) each participant will be given \$15 at the time of each neurocognitive assessment and (2) a Mayo parking voucher at the time of each MRI assessment. The compensation is intended to encourage patients to continue study related tests by providing partial compensation for travel expenses.

## 6 STUDY INTERVENTION

### 6.1 STUDY INTERVENTION(S) ADMINISTRATION

#### 6.1.1 STUDY INTERVENTION DESCRIPTION

##### ***Study intervention***

Participants will be randomly assigned 1:1 to one of 2 treatment arms. Randomization will be stratified by decade of age and gender. Drug administration will be according to the FDA approved labeling.

*Treatment arm 1 (Apixaban arm)* will receive Apixaban 5 mg twice daily unless patient has any 2 of the following: Age  $\geq 80$  years, body weight  $\leq 60$  kg, or serum creatinine  $\geq 1.5$  mg/dL, then reduce dose to 2.5 mg twice daily.

For patients receiving a non-Apixaban anticoagulant at the time of enrollment, the following procedure will be followed to convert them to Apixaban:

Conversion from warfarin to apixaban: Discontinue warfarin and initiate apixaban when INR is <2

Conversion from other non-warfarin anticoagulants (oral or parenteral) to apixaban: Discontinue the other non-warfarin anticoagulant and begin taking apixaban at the usual time of the next scheduled dose of the other non-warfarin anticoagulant.

*Treatment arm 2 (Warfarin arm)* will receive dose adjusted warfarin to maintain INR between 2 – 3. Dose adjustment performed using a standardized nomogram at an anti-coagulation clinic will be encouraged but not required. Interval of INR testing will be determined by the treating physician.

For patients receiving a non-Apixaban oral anticoagulant at the time of enrollment, the following procedure will be followed to convert them to Warfarin: The anticoagulant will be continued until the INR is  $\geq 2$ .

For patients receiving a parenteral anticoagulant at the time of enrollment to the warfarin arm, the treating physician will determine the need for ‘bridging’ anticoagulation until the INR is therapeutic.

---

## 6.1.2 DOSING AND ADMINISTRATION

### **Apixaban**

5 mg twice daily unless patient has any 2 of the following: Age  $\geq 80$  years, body weight  $\leq 60$  kg, or serum creatinine  $\geq 1.5$  mg/dL, then reduce dose to 2.5 mg twice daily. Oral administration.

For patients qualifying for Apixaban 5 mg twice daily, the dose of Apixaban will be decreased by 50% when co-administered with drugs that are strong dual inhibitors of CYP3A4 and P-gp (e.g., ketoconazole, itraconazole, ritonavir, or clarithromycin).

Need for dose adjustment will be performed at the 1 year mark or sooner if the patient’s age, weight or creatinine warrant this.

### **Warfarin**

Dose adjusted to maintain INR between 2 – 3. Dose adjustment performed using a standardized nomogram at an anti-coagulation clinic will be encouraged but not required. Interval of INR testing will be determined by the treating physician. Oral administration.

## 6.2 PREPARATION/HANDLING/STORAGE/ACCOUNTABILITY

*Apixaban arm:* The drug will be provided by and paid for by BMS / Pfizer. The drug will be provided to Mayo Clinic. It will be distributed to patients once every 6 months via mail by the Mayo Clinic Pharmacy. Apixaban will be stored at 20°C to 25°C (68°F-77°F); excursions permitted between 15°C and 30°C (59°F-86°F) per the drug labeling.

*Warfarin arm:* Warfarin will be prescribed by the treating physician. INR monitoring and dose adjustment will also be performed by the treating physician / assigned anticoagulation clinic. Warfarin will not be provided or paid for by the study.

### 6.3 MEASURES TO MINIMIZE BIAS: RANDOMIZATION AND BLINDING

Study participants will be randomized 1:1 to either Apixaban or dose adjusted Warfarin. Placebo pills will not be administered. Participants, the principal investigator and study coordinator will not be blinded to treatment assignment. Study personnel administering and interpreting the MRI images and cognitive function assessment will be blinded to treatment assignment. Randomization codes will be generated at the time of enrollment and each individual's cognitive function tests and MRI scan identified by this code. Blinding of participants in this study will require the use of placebo and INR testing in both groups, which will be burdensome to the patient and will not affect the outcomes of cognitive function or MRI findings.

Unblinding of personnel to treatment assignment will be performed only when there is a serious adverse event such as intra-cranial hemorrhage.

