### ***Measurement of secondary endpoint: Mild cognitive impairment or dementia***

The CDR score (range 0–3) will be assessed in addition to the results of the neuropsychological testing. A team of Neurologist and Neuropsychometrist will assign a diagnosis of normal cognition or mild cognitive impairment or dementia to each subject at each time point. This team will be blinded to treatment assignments. Each assessment of an individual patient will be assessed independent of prior assessments. The definitions used are as follows:

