#### *Dementia*

Subjects with a CDR 1 will be classified as demented if they meet DSM-V criteria for 'major neurocognitive disorder' as follows:

1. Evidence of significant cognitive decline from a previous level of performance in one or more cognitive domains based on:
  - a. Concern of the individual, a knowledgeable informant, or the clinician that there has been a significant decline in cognitive function; and
  - b. A substantial impairment in cognitive performance, preferably documented by standardized neuropsychological testing.
2. The cognitive deficits interfere with independence in everyday activities.
3. The cognitive deficits do not occur exclusively in the context of delirium and are not better explained by another mental disorder.

For subjects with CDR 0.5, a committee of the examining neuropsychologist and physician will critically examine the available tests to determine whether the DSM-V criteria for dementia or MCI are met.

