#### *Mild cognitive impairment*

The criteria for diagnosis of MCI are: cognitive concern expressed by a physician, informant, participant or nurse; cognitive impairment in 1 or more domains; normal functional activities and not demented. Subjects with MCI can have a CDR of 0 or 0.5; however, the final diagnosis of MCI will not be based exclusively on the CDR but rather on all available data. A committee of the examining neuropsychologist and physician will critically examine the available tests to determine whether the criteria for MCI are met.

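### Section 6.3's assurance that participant blinding would not affect cognitive outcomes is unsupported for the secondary MCI/dementia endpoint, which depends on concerns voiced by people who know, or may know, the arm

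*Combined protocol and SAP*

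**What the plan says.** Section 6.3 describes an open-label trial with blinded assessment. "Participants, the principal investigator and study coordinator will not be blinded to treatment assignment". On the other side, "Study personnel administering and interpreting the MRI images and cognitive function assessment will be blinded to treatment assignment". The reason given for not blinding participants is that it would require placebo and INR testing in both arms, "which will be burdensome to the patient and will not affect the outcomes of cognitive function or MRI findings". No exception is made for MCI or dementia.

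Section 8.1 (repeated in Sections 3 and 9.1) defines MCI by several elements that must all be present: "cognitive concern expressed by a physician, informant, participant or nurse; cognitive impairment in 1 or more domains; normal functional activities and not demented". It adds that "the final diagnosis of MCI will not be based exclusively on the CDR but rather on all available data". The first dementia criterion also has a reported element, 1a: "Concern of the individual, a knowledgeable informant, or the clinician that there has been a significant decline in cognitive function; and" it must be accompanied by impaired performance (1b).

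The Clinical Dementia Rating (CDR) and the functional questionnaire are completed by interviewing an informant whom the participant names and sees at least weekly. A team of neurologist and neuropsychometrist assigns the diagnosis, and "This team will be blinded to treatment assignments". Participants who cannot attend are classified by telephone (Sections 7.3 and 9.1). Section 9.4.1 plans a Cox model for MCI/dementia and no analysis that leaves out the reported elements.

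**The concern.** Blinding the people who decide protects the decision, not the information they are given. If a participant, relative or treating clinician is readier to voice concern in one arm, two participants with identical test impairment can receive different diagnoses, even from a team that does not know the arm.

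The plan contains conditions in which that could happen. The stated hypothesis is that apixaban slows cognitive decline, and the purposes of the study are explained at consent (Section 10.1.1). Warfarin patients have INR monitoring through the treating physician or an anticoagulation clinic, whereas apixaban is mailed every six months (Section 6.2). The arms may therefore differ in how often a clinician has occasion to note a concern.

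At stake is what the MCI/dementia result can support. With a single Cox analysis and no record by arm of who voiced concern, a difference between arms could not be separated from a difference in reporting.

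**Working it through.** **Who knows the arm, element by element**

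| Element of the diagnosis | Source | Kept unaware of the arm? |
|---|---|---|
| Concern of the participant | Participant | No (6.3) |
| Concern of a treating physician | Prescribes and adjusts warfarin (6.2) | No |
| Concern of an informant; CDR; functional questionnaire | Weekly contact named by the participant (8.1) | No provision; knowledge of the arm is an inference |
| Impairment in a domain | In-person battery | Yes, testers and interpreters (6.3) |
| Final diagnosis | Neurologist and neuropsychometrist (8.1) | Yes |

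An expressed concern is necessary but not sufficient. In person, reporting bias can act only on those whom the blinded battery shows to be impaired. By telephone, the modified Telephone Interview of Cognitive Status (TICS-M) and two informant instruments replace the four-domain battery, so that restraint is weaker.

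**Figures in the plan.** No incidence, concern rate or power is stated for MCI/dementia. The 140 per arm comes from the primary endpoint and reproduces: 0.05 / (0.16 × √(2/140)) = 2.615, and Φ(2.615 − 1.645) = 0.834, in line with the stated power above 80%.

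**Illustration (all rates assumed).** There is no drug effect. A proportion q of each arm is impaired on testing by two years. A concern is voiced for a share cA (apixaban) or cW (warfarin) of those impaired. All 140 per arm are assessed in person.

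- Diagnosed proportions: pA = q × cA and pW = q × cW.
- Apparent hazard ratio: ln(1 − pA) / ln(1 − pW).
- Chance of significance for apixaban at one-sided 0.05: Φ[((pW − pA) − 1.645 × s0) / s1], with s0 = √(p̄(1 − p̄) × 2/140), p̄ the mean of pA and pW, and s1 = √((pA(1 − pA) + pW(1 − pW))/140).

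Example, q = 20%, cA = 60%, cW = 80%: pA = 0.12 and pW = 0.16. The hazard ratio is ln 0.88 / ln 0.84 = 0.733. With s0 = 0.0415 and s1 = 0.0414, the chance is Φ[(0.04 − 1.645 × 0.0415)/0.0414] = Φ(−0.68) = 0.25.

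| q | cA v cW | Diagnoses per 140 | Apparent hazard ratio | Chance of significance for apixaban |
|---|---|---|---|---|
| 10% | 70% v 80% | 9.8 v 11.2 | 0.870 | 9% |
| 20% | 70% v 80% | 19.6 v 22.4 | 0.865 | 12% |
| 30% | 70% v 80% | 29.4 v 33.6 | 0.859 | 15% |
| 10% | 60% v 80% | 8.4 v 11.2 | 0.742 | 16% |
| 20% | 60% v 80% | 16.8 v 22.4 | 0.733 | 25% |
| 30% | 60% v 80% | 25.2 v 33.6 | 0.723 | 34% |

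With equal concern the chance is the nominal 5%. One-sided testing is stated only for the power calculation; for a two-sided 0.05 test the nominal 2.5% in apixaban's favour becomes 5% to 9% (70% v 80%) or 10% to 23% (60% v 80%). If concern were voiced more often on apixaban, the hazard ratios would be the reciprocals, 1.15 to 1.16 and 1.35 to 1.38, and the error would run against apixaban.

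**The case against.** The strongest reply is that open label with blinded assessment is a deliberate design and that the exposure is bounded. Cognitive testing and diagnosis are blinded. MCI needs impairment in a domain as well as concern, and dementia needs more. Concern may come from any of four sources, so one quiet source does not remove a diagnosis. The sentence in 6.3 can be read as meaning the cognitive scores, since MCI/dementia is named separately elsewhere. The primary analysis of longitudinal scores needs no voiced concern and would be read beside the MCI/dementia result.

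Most of that stands and limits the point. It does not answer it: the sentence as written carries no restriction to scores, and the primary analysis does not show whether a given MCI/dementia difference arose from reporting.

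Three stronger readings are tempting and are not supported.

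- **The committee is unblinded.** Section 8.1 describes the committee for CDR 0.5 and MCI in words that differ from the blinded team and does not repeat the blinding. But those definitions are introduced as the ones the blinded team uses, and 6.3 covers personnel who interpret the cognitive assessment. What remains is a wording gap.
- **The chart reveals the arm to the committee.** No section says the committee opens the medical record. Reliance on all available data is set against reliance on the CDR alone, and the next sentence speaks of examining tests. Cognitive tests and scans carry a code (6.3), and cognitive data are stored apart from clinical data (10.1.6.1). It is a possibility to close off, not a documented fault.
- **The result is biased towards apixaban.** Both mechanisms described above would point that way if they operated, but nothing in the documents shows that they do.

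**Conclusion.** The assurance in 6.3 is not supported for MCI/dementia, because the plan's own definitions require reports from people who know, or are not kept from knowing, the treatment. Blinded adjudication does not remove differential reporting, and the telephone route is the most exposed.

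Size and direction cannot be derived. The table shows only that a gap of 10 to 20 percentage points in voiced concern, if it occurred, would move the apparent hazard ratio to between 0.72 and 0.87, or to the reciprocals if reversed. It rests on assumed impairment and concern rates, 140 assessed in person per arm and no drug effect. That informants know the arm is also an inference.

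Blinded test scores, and so the primary endpoint, and blinded MRI reading are not in question. Because the endpoint is secondary and the remedy cheap, this is a change that should be made rather than a flaw that undermines the trial.

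**What to change.** 1. **Section 6.3.** Limit the sentence to test scores obtained blind and MRI read blind, and state that open-label reporting may affect the MCI/dementia endpoint.
2. **Section 9.4.1.** Add a sensitivity analysis of incident impairment defined only by the blinded in-person domain z-scores, without the concern criterion or informant items. The plan gives no cut-off for domain impairment, so fix one before any data by arm are seen. State that participants followed only by telephone cannot contribute after their last in-person test. Report by arm the rate and source of expressed concern and the number classified by telephone.
3. **Sections 8.1 and 9.1.** State that the committee for CDR 0.5 and MCI is the blinded team and does not include the treating physician. Its material should keep the record of expressed concern, since the definitions cannot be applied without it, but have drug names, INR results and anticoagulation-clinic notes removed.

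The cost is some wording, a form entry for who voiced a concern if none exists, redaction by the coordinator (already unblinded), and one analysis of data already being collected. No visits or participants are added. The downside is that a score-only definition is clinically less specific, so it belongs as a sensitivity analysis and not as a replacement. Redaction protects the committee's blinding but does not correct unequal reporting, which is why the second change is also needed.

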## 7 STUDY INTERVENTION DISCONTINUATION AND PARTICIPANT DISCONTINUATION/WITHDRAWAL

### 7.1 DISCONTINUATION OF STUDY INTERVENTION

Discontinuation from study intervention (anticoagulant use) does not mean discontinuation from the study, and remaining study procedures should be completed as indicated by the study protocol. If a clinically significant finding is identified (including, but not limited to changes from baseline) after enrollment, the investigator or qualified designee will determine if any change in participant management is needed. Any new clinically relevant finding will be reported as an adverse event (AE). Events that may trigger include:

1. Major bleeding event. The anticoagulant will be discontinued and future management of anticoagulant will be decided by the treating physician. The patient will not be re-challenged with anticoagulant as part of the study protocol.
2. Ischemic Stroke / TIA. Management of anticoagulant in the first month following an ischemic stroke / TIA will be determined by the treating physician. Following this, a decision regarding whether to continue study intervention will be made in consultation with the treating physician and the patient. Whether the anticoagulant was being used in a therapeutic fashion at the time of event will be part of this discussion.
3. Hemorrhagic stroke. The study intervention will be discontinued and future anticoagulation decision will be made by the treating physician.
4. Participants will be strongly encouraged by the study staff to remain on treatment assigned through randomization and to comply with the study protocol and follow-up. However, participants or their physician may voluntarily discontinue study intervention or change OAC treatment at any time. Study staff will make every effort to discourage this.

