### **Brain MRI imaging to assess burden of cerebral infarcts and cerebral microbleeds**

#### **MR Imaging of brain**

Cerebral MRI will be performed *without* gadolinium contrast using a 3 Tesla scanner at enrollment and at 2 years. If a subject is withdrawn or withdraws prior to the completion of follow-up, an attempt to obtain MRI prior to withdrawal will be made. The following imaging sequences will be performed per standard protocols at our institution: (1) sagittal T1-weighted, (2) axial T2-weighted fast spin echo (FSE), (3) axial T2-weighted fluid-attenuated inversion recovery (FLAIR), (4) axial gradient echo (GRE), (5) axial diffusion tensor-tracer imaging (DTI), (7) 3-dimensional magnetization prepared rapid gradient-echo (MPRAGE) sequence and (8) Axial SWAN (T2 Star Weighted Angiography).

The MRI will be read by a board certified Radiologist who is blinded to treatment assignment.

A new cerebral infarct will be defined as an unequivocal focus of hyperintensity to gray matter on DTI images. GRE and MPRAGE sequences will be used to quantitate the cerebral microbleeds. Cerebral volume analysis will be performed for total cerebral and hippocampal volume using standardized software. The number, size and location of new cerebral infarcts (cortical vs. subcortical and specific anatomic location of infarct) and cerebral microbleeds (lobar vs subhemispheric and specific anatomic location of infarct) will be determined and documented in a CRF.

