### 8.3.2 DEFINITION OF SERIOUS ADVERSE EVENTS (SAE)

A **Serious Adverse Event (SAE)** is any untoward medical occurrence that at any dose:

- results in death
- is life-threatening (defined as an event in which the participant was at risk of death at the time of the event; it does not refer to an event which hypothetically might have caused death if it were more severe)
- requires inpatient hospitalization or causes prolongation of existing hospitalization (see **NOTE** below)
- results in persistent or significant disability/incapacity
- is a congenital anomaly/birth defect
- is an important medical event (defined as a medical event(s) that may not be immediately life-threatening or result in death or hospitalization but, based upon appropriate medical and scientific judgment, may jeopardize the subject or may require intervention [eg, medical, surgical] to prevent one of the other serious outcomes listed in the definition above.) Examples of such events include, but are not limited to, intensive treatment in an emergency room or at home for allergic bronchospasm; blood dyscrasias or convulsions that do not result in hospitalization.)
- Suspected transmission of an infectious agent (eg, pathogenic or nonpathogenic) via the study drug is an SAE.

Although pregnancy, overdose, adverse events of special interest, and cancer are not always serious by regulatory definition, these events must be handled as SAEs.

Any component of a study endpoint that is considered related to study therapy should be reported as an SAE (eg, death is an endpoint, if death occurred due to anaphylaxis, anaphylaxis must be reported).

The following hospitalizations are not considered SAEs in BMS clinical studies:

- a visit to the emergency room or other hospital department < 24 hours, that does not result in admission (unless considered an important medical or life-threatening event)
- elective surgery, planned prior to signing consent
- admissions as per protocol for a planned medical/surgical procedure
- routine health assessment requiring admission for baseline/trending of health status (eg, routine colonoscopy)
- Medical/surgical admission other than to remedy ill health and planned prior to entry into the study. Appropriate documentation is required in these cases.

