#### 8.3.11 REPORTING EVENTS TO PARTICIPANTS

Study participants will be informed of any adverse events or incidental findings through a letter or phone call. In the case of a serious adverse event, the participant will be informed through a phone call within 48 hours of the occurrence. If patient is not reachable, attempts will be made to reach the alternative contact person and the primary treating physician, whose contact information will be sought from the subject at enrollment. The participant will be encouraged to seek care with the primary

treating physician to treat SAEs and to assess any incidental findings, such as findings on brain imaging that require further assessment.

Interpretation of the brain MRI will be performed by a board certified clinical Radiologist and a report generated in the patient's clinical record. This report will be shared with the participant through a letter. This report is however different from the more detailed analysis of the sequences that will be performed by the study Radiologist in a blinded fashion. The results of the cognitive function testing will be shared with individual participants only in the event of diagnosis of dementia, which is expected to have an impact on the overall management of the subject. The aggregate results of the study will be shared with all the participants once published in a peer review journal.

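### The unblinding rule in section 6.3 lets outcome assessors learn the allocation after a serious adverse event, with no stated safety purpose; a one-sentence change closes this minor route to bias

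*Combined protocol and SAP*

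**What the plan says.** Section 6.3 sets out who knows the allocation. On one side, "Participants, the principal investigator and study coordinator will not be blinded to treatment assignment". On the other, "Study personnel administering and interpreting the MRI images and cognitive function assessment will be blinded to treatment assignment". Section 4.1 repeats the blinding of testers and readers. Section 8.1 adds two specific statements. For the MRI, "The MRI will be read by a board certified Radiologist who is blinded to treatment assignment". For the neurologist and neuropsychometrist who assign the MCI or dementia diagnosis, "This team will be blinded to treatment assignments". None of these statements carries an exception.

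Section 6.3 then closes with an exception: "Unblinding of personnel to treatment assignment will be performed only when there is a serious adverse event such as intra-cranial hemorrhage". It does not say which personnel, for what purpose, or who makes later assessments of that participant.

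Three other places bear on the rule:
- Section 7.1 says that stopping the drug is not leaving the study, and that "remaining study procedures should be completed as indicated by the study protocol". Participants who change anticoagulant are withdrawn, and their cognition and MRI are assessed at withdrawal if more than 6 months have passed since the last assessment.
- Section 8.3.2 counts as serious any event that "requires inpatient hospitalization or causes prolongation of existing hospitalization".
- Section 8.3.11 separates the clinical MRI report, which goes to the medical record and the participant, from the detailed study reading "performed by the study Radiologist in a blinded fashion".

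**The concern.** An emergency unblinding rule normally serves a clinician who must treat a patient without knowing the drug. In this trial the participant, the principal investigator and the coordinator know the drug from the start. The people left to unblind are those who score the outcomes, and they are the people whose ignorance of the allocation protects the comparison.

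The blind would be lifted selectively, in participants who have just had a serious event. Some of them will be assessed again. MCI and dementia are committee judgements that draw on all available data, and infarct and microbleed calls are reader judgements. A reader who knows the drug and the hypothesis could lean, without meaning to, in the hypothesised direction. Only one post-baseline MRI is scheduled, at 2 years, so one unblinded reading could be a participant's entire MRI follow-up outcome.

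**Working it through.** **Step 1. Who can be unblinded?** Setting the sections side by side:

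| Role | Status in the documents |
|---|---|
| Participant, principal investigator, coordinator | Not blinded (6.3) |
| Treating physician | Prescribes and adjusts warfarin (6.2); decides on anticoagulation after an event (7.1); no blinding stated |
| Data and Safety Monitoring Board (DSMB) | Reviews safety data for each arm (10.1.5); no blinding stated |
| Cognitive testers, MRI personnel and reader | Blinded (4.1, 6.3, 8.1, 8.3.11) |
| MCI/dementia team | Blinded (8.1, 9.1) |

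Only the last two rows describe someone who can be unblinded, and both are outcome assessors. The text does not name them. This is an inference by elimination.

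**Step 2. Is a safety purpose given?** None is stated. Anticoagulation after a bleed or stroke is decided by or with the treating physician (7.1). A DSMB physician grades severity and relationship to drug (8.3.3.1, 8.3.3.2). The MRI is screened for asymptomatic bleeding (8.2), but a reader can report a bleed without knowing the drug, and a separate clinical report exists (8.3.11).

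**Step 3. Can readings follow the event?** Yes: scheduled visits continue after the drug is stopped, and withdrawal readings are made under the 6-month condition (7.1).

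**Step 4. The plan's own design figure.** Section 9.2 uses a difference of 0.05/year, SD 0.16, one-sided alpha 0.05 and 140 per arm. The standard error is 0.16 × √(2/140) = 0.0191. Then 0.05/0.0191 = 2.61, 2.61 − 1.645 = 0.97, and power is about 0.83. This agrees with the stated power of more than 80%. The present point does not change it.

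**Step 5. How many participants?** The only event rate near the trigger is the 1 to 3% per year major bleeding on warfarin in section 2.3.1. Over 2 years:
- 1%: 1 − 0.99² = 0.0199, and 140 × 0.0199 = 2.8
- 3%: 1 − 0.97² = 0.0591, and 140 × 0.0591 = 8.3

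That is about 3 to 8 of 140 warfarin participants. If the same rate is assumed in both arms, it is 5.6 to 16.5 of 280, or about 6 to 17. If any serious event, including hospitalisation, triggered unblinding, the number would be larger, but no overall rate is given. Purely as an assumption, 10% to 40% of 280 would be 28 to 112.

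**Step 6. Effect on the primary mean (illustrative).** If a fraction f of one arm is read with a slope shift b, and nobody in the other arm is, the difference between arms moves by f × b. The values of b are assumptions: 0.05/year (the whole target effect) and 0.16/year (one SD).

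| f | b = 0.05/year | b = 0.16/year |
|---|---|---|
| 2% | 0.001 (2% of 0.05) | 0.0032 (6%) |
| 6% | 0.003 (6%) | 0.0096 (19%) |

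The right-hand column needs every affected participant's slope to be misread by a full SD, all in the same arm.

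**The case against.** The strongest reply is that the sentence is a limit. It says when unblinding may occur; it does not order that assessors be told after each event, and its one example is a severe neurological event. This stands: the rule permits unblinding and does not require it. The recipients are also inferred, and other staff may have been in mind. That too is fair, but the documents describe no other blinded group, and if someone else was meant the sentence should say so.

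The reply also has force on exposure. A bleed found on the 2-year MRI is followed by no further scheduled scan. Participants who change anticoagulant are withdrawn and censored, without repeat testing if they were assessed within 6 months. Exposure is therefore limited, though section 7.1 keeps it above zero.

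A reader might infer more than the documents support:
- *That assessor blinding is the only protection.* It is not. The primary endpoint uses standardised tests converted to normative scores, tests and scans carry a code, and each diagnosis is made independently of earlier ones.
- *That unblinding could have no safety use at all.* The documents do not describe the clinical roles of the neurologist or examining physician. What can be said is that no purpose is given.
- *That the loss of blinding would clearly differ by arm.* Section 2.2 reports less intracranial haemorrhage on apixaban, so it may. But the bleeding-related discontinuation rates in section 2.3.1, 1.7% and 2.5%, give 140 × 0.008 = 1.1, or about one participant per arm of 140. A material imbalance is not shown.

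**Conclusion.** The concern holds as a minor, cheaply removed weakness. As written, section 6.3 allows outcome assessors to be unblinded after a serious adverse event, states no safety reason, and provides no replacement reader. The bias route runs mainly through MCI/dementia and MRI lesion calls.

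The size is uncertain. If only major bleeds trigger the rule, about 3 to 8 of 140 warfarin participants are affected over 2 years. The primary difference would then move by about 0.001 to 0.003/year against a target of 0.05/year, assuming that each affected slope shifts by the whole target effect and that all the shift falls in one arm. A wider trigger would reach more participants, by an amount the documents cannot fix.

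A reader might conclude that the rule could account for a fifth of the design effect. With the same 0.05/year shift, that needs 20% of one arm affected and none of the other (0.20 × 0.05 = 0.01/year). Nothing in the documents supports that fraction. The judgement that outcome assessors are the recipients rests on elimination, not on explicit text.

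**What to change.** Replace the last sentence of section 6.3 with a statement to this effect: personnel who administer or interpret cognitive tests or MRI, and the MCI/dementia team, remain blinded after any adverse event; safety reporting and participant management use the allocation already known to unblinded staff. If the sponsor meant the sentence for some other blinded role, name that role and the purpose.

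Add that any accidental unblinding of an assessor is recorded with its date and, where the existing blinded team allows, that another member makes the later reading.

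The cost is one or two sentences and the small burden of keeping the log. The sample size, visits, assessments and clinical care rules do not change.
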